6.2.1. Management of Atezolizumab-Specific Adverse Events

Beginning with the implementation of Amendment 7, toxicities associated or possibly associated with atezolizumab treatment, including non-immune mediated adverse events, should be managed according to local regulatory approvals and standard of care guidelines.^{50,51} Additional tests, such as autoimmune serology or biopsies, should be used to determine a possible immunogenic etiology.

Although most immune-mediated adverse events observed with immunomodulatory agents have been mild and self-limiting, such events should be recognized early and treated promptly to avoid potential major complications. Discontinuation of atezolizumab may not have an immediate therapeutic effect and, in severe cases, immune-mediated toxicities may require acute management with topical corticosteroids, systemic corticosteroids, or other immunosuppressive agents.

The investigator should consider the benefit-risk balance a given subject may be experiencing prior to further administration of atezolizumab. Atezolizumab should be permanently discontinued in subjects with life-threatening, immune-mediated adverse events. Specific guidelines for immune-mediated events are provided in [Attachment 7](#).

For all other non-immune mediated adverse events, including infections, atezolizumab should be withheld for Grade 3 or higher toxicity with the following exceptions:

- Grade 3 nausea that responds to antiemetic treatment within 7 days
- Grade 3 vomiting that responds to antiemetic treatment within 7 days
- Grade 3 diarrhea that responds to antidiarrheal treatment within 7 days
- Grade 3 fatigue that was present at baseline or that lasts for <7 days after the last administration of atezolizumab
- Grade 3 asthenia that was present at baseline or that lasts for <7 days after the last administration of atezolizumab

Administration of atezolizumab may be restarted upon recovery from toxicity to Grade 1 or baseline.

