6.2. Atezolizumab

Beginning with the implementation of Amendment 7, subjects who are deriving clinical benefit from atezolizumab monotherapy, but do not have access to commercial atezolizumab, may continue treatment under the supervision of the treating investigator in accordance with local regulatory approvals and standard of care guidelines.^{50,51} Prior to the administration of atezolizumab, investigators will be required to submit documentation of subject response and clinical status to the Sponsor, either electronically or via facsimile.

For subjects in Arm A, atezolizumab will be administered at 1,200 mg IV on Day 1 of every 21-day cycle. For subjects in the Safety Run-in and Arm B, atezolizumab will be administered on Day 2 of Cycle 1 and on Day 1 of every 21-day cycle thereafter. Atezolizumab should always be administered after daratumumab. A delay in daratumumab dosing will result in a subsequent delay in atezolizumab dosing. All study subjects should continue to be treated until one or more treatment discontinuation criteria are met (Section 10.2).

Refer to the SIPPM for detailed instructions on drug preparation, storage, and administration. Dose modifications to atezolizumab are not permitted. Guidelines for treatment interruption or discontinuation and the management of specific adverse events are provided below.

Subjects may temporarily suspend study treatment for up to 105 days beyond the last dose if they experience an adverse event that requires a dose to be withheld. If atezolizumab is withheld because of adverse events for >105 days, then the subject will be discontinued from atezolizumab treatment and will be followed for safety and efficacy as specified in Section 9.1.5.

If, in the judgment of the investigator, the subject is likely to derive clinical benefit from atezolizumab after a hold of >105 consecutive days that is not adverse event-related, study drug may be restarted with the approval of the Sponsor.

If a subject must be tapered off steroids used to treat adverse events, atezolizumab may be withheld for additional time beyond 105 days from the last dose until steroids are discontinued or reduced to prednisone dose (or dose equivalent) ≤ 10 mg/day. The acceptable length of interruption will depend on agreement between the investigator and the Sponsor.

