10.2. Discontinuation of Study Treatment/Withdrawal from the Study

Discontinuation of Study Treatment

A subject will not be automatically withdrawn from the study if he or she has to discontinue treatment. The End-of-Treatment Visit and Follow-up visit assessments should continue as specified in the Time and Events Schedules.

A subject's study treatment must be discontinued if:

- The investigator believes that for safety reasons or tolerability reasons (eg, adverse event) it is in the best interest of the subject to discontinue study treatment
- The subject becomes pregnant
- The subject (or the subject's legally acceptable representative) withdraws consent for administration of study treatment
- The subject experiences unacceptable toxicity, including IRRs described in Section 6.3
- The subject missed more than 2 consecutive planned doses due to daratumumab-related AEs
- The subject missed more than 105 consecutive treatment days due to atezolizumab-related AEs
- The subject experiences confirmed disease progression (per RECIST 1.1), see Table 12.
- A subject who experiences a second primary malignancy that cannot be treated by surgery alone must be withdrawn from the study. However, a subject who develops a malignancy that can be cured surgically may continue to receive the assigned study treatment and should continue to be followed for subsequent progression of NSCLC.

The primary reason for discontinuation of study treatment is to be recorded in the CRF.

Withdrawal From the Study

A subject will be withdrawn from the study for any of the following reasons:

- Lost to follow-up
- Withdrawal of consent to study participation
- Pregnancy
- Second primary malignancy (see Discontinuation of Study Treatment for additional details)
- Death
- The study investigator, for any reason, stops the subject's participation in the study
- Sponsor terminated the study

Before a subject is lost to follow-up, every reasonable effort must be made by the study-site personnel to contact the subject and determine the reason for discontinuation/withdrawal. The measures taken to follow up must be documented.

When a subject withdraws before completing the study, the reason for withdrawal is to be documented in the CRF and in the source document. Study drug assigned to the withdrawn subject may not be assigned to another subject. Subjects who withdraw will not be replaced. If a subject discontinues from treatment, end-of-treatment assessments should be obtained.

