12.1.3. Severity Criteria

The severity assessment for an adverse event or serious adverse event should be completed using the NCI-CTCAE Version 4.03. Any adverse event or serious adverse event not listed in the NCI-CTCAE Version 4.03 will be graded according to investigator clinical judgment by using the standard grades as follows:

Grade 1 (Mild): Awareness of symptoms that are easily tolerated, causing minimal discomfort and not interfering with everyday activities

Grade 2 (Moderate): Sufficient discomfort is present to cause interference with normal activity

Grade 3 (Severe): Extreme distress, causing significant impairment of functioning or incapacitation. Prevents normal everyday activities

Grade 4: Life-threatening or disabling adverse event

Grade 5: Death related to the adverse event

The investigator should use clinical judgment in assessing the severity of events not directly experienced by the subject (eg, laboratory abnormalities).

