Attachment 7: Management Guidelines for Atezolizumab

Management guidelines for toxicities associated or possibly associated with atezolizumab are provided as follows:

- Pulmonary events, please see [Table 13](#)
- Hepatic events, please see [Table 14](#)
- Gastrointestinal events, please see [Table 15](#)
- Endocrine events, please see [Table 16](#)
- Ocular events, please see [Table 17](#)
- Pancreatic events, please see [Table 18](#)
- Immune-mediated myocarditis, please see [Table 19](#)
- Dermatologic events, please see [Table 20](#)
- Neurologic disorders and meningoencephalitis, please see [Table 21](#)
- Systemic immune activation events, please see [Table 22](#)
- Immune-related Nephritis, please see [Table 23](#).

Table 13: Management Guidelines for Pulmonary Events, Including Pneumonitis

Event	Management
Pulmonary event, Grade 1	
 • Continue atezolizumab and monitor closely. • Re-evaluate on serial imaging. • Consider subject referral to pulmonary specialist.
Pulmonary event, Grade 2	
 • Withhold atezolizumab for up to 12 weeks after event onset.^a • Refer subject to pulmonary and infectious disease specialists and consider bronchoscopy or BAL. • Initiate treatment with 1–2 mg/kg/day oral prednisone or equivalent. • If event resolves to Grade 1 or better, resume atezolizumab.^b • If event does not resolve to Grade 1 or better while withholding atezolizumab, permanently discontinue atezolizumab and contact Sponsor.^c
Pulmonary event, Grade 3 or Grade 4	
 • Permanently discontinue atezolizumab and contact the Sponsor.^c • Bronchoscopy or BAL is recommended. • Initiate treatment with 1–2 mg/kg/day oral prednisone or equivalent. • If event does not improve within 48 hours after initiating corticosteroids, consider adding an immunosuppressive agent. • If event resolves to Grade 1 or better, taper corticosteroids over ≥ 1 month.

BAL=bronchoscopic alveolar lavage; IVIG=intravenous immunoglobulin

- Atezolizumab may be withheld for a longer period of time (ie, >12 weeks after event onset) to allow for corticosteroids (if initiated) to be reduced to ≤ 10 mg/day oral prednisone or equivalent. The acceptable length of the extended period of time must be agreed upon by the investigator and the Sponsor.

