Symptomatic adrenal insufficiency, Grade 2-4	
 • Withhold atezolizumab for up to 12 weeks after event onset.^b • Refer subject to endocrinologist. • Perform appropriate imaging. • Initiate treatment with 1–2 mg/kg/day IV methylprednisolone or equivalent and convert to 1–2 mg/kg/day oral prednisone or equivalent upon improvement. • If event resolves to Grade 1 or better, resume atezolizumab.^c • If event does not resolve to Grade 1 or better while withholding atezolizumab, permanently discontinue atezolizumab and contact Sponsor.^a
Hyperglycemia, Grade 1 or 2	
 • Continue atezolizumab. • Initiate treatment with insulin if needed. • Monitor for glucose control.
Hyperglycemia, Grade 3 or 4	
 • Withhold atezolizumab. • Initiate treatment with insulin. • Monitor for glucose control. • Resume atezolizumab when symptoms resolve and glucose levels are stable.

Hypophysitis pan-hypopituitarism), Grade 2-3	
 • Withhold atezolizumab for up to 12 weeks after event onset.^b • Refer subject to endocrinologist. • Perform brain MRI (pituitary protocol). • Initiate treatment with 1-2 mg/kg/day IV methylprednisolone or equivalent and convert to 1-2 mg/kg/day oral prednisone or equivalent upon improvement. • If event resolves to Grade 1 or better, resume atezolizumab.^c • If event does not resolve to Grade 1 or better while withholding atezolizumab, permanently discontinue atezolizumab and contact Sponsor.^a • For recurrent hypophysitis, treat as a Grade 4 event.
Hypophysitis pan-hypopituitarism), Grade 4	
 • Permanently discontinue atezolizumab and contact the Sponsor.^a • Refer subject to endocrinologist. • Perform brain MRI (pituitary protocol). • Initiate treatment with 1-2 mg/kg/day IV methylprednisolone or equivalent and convert to 1-2 mg/kg/day oral prednisone or equivalent upon improvement.^b • Initiate hormone replacement therapy if clinically indicated.

TSH=thyroid-stimulating hormone

- a. Resumption of atezolizumab may be considered in subjects who are deriving benefit and have fully recovered from the immune-related event. Subjects can be rechallenged with atezolizumab only after approval has been documented by both the investigator (or an appropriate delegate) and the Sponsor.

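### Section 6.2.1 and Attachment 7 give opposite stop-or-resume instructions for life-threatening adrenal insufficiency, and Sections 6.2, 10.2 and Attachment 7 run the atezolizumab hold limit on different clocks

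*Protocol*

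**What the plan says.** **Stopping for severe immune events.** Section 6.2.1 says: "Atezolizumab should be permanently discontinued in subjects with life-threatening, immune-mediated adverse events". The sentence has no exception. The next one refers the reader to Attachment 7 for specific guidance.

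In Attachment 7, Table 16 groups "Symptomatic adrenal insufficiency, Grade 2-4" in one row. The drug is withheld, and then: "If event resolves to Grade 1 or better, resume atezolizumab". The Grade 3 or 4 hyperglycemia row of the same table ends: "Resume atezolizumab when symptoms resolve and glucose levels are stable". Table 18 also lets Grade 3 or 4 amylase or lipase elevation be withheld and resumed. Footnotes attached to permanent discontinuation in Tables 13 to 21 allow rechallenge in a subject who is benefiting and has fully recovered, with documented approval from both the investigator and the Sponsor.

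**Length of hold.** Section 6.2: "Subjects may temporarily suspend study treatment for up to 105 days beyond the last dose", for an adverse event that requires withholding. Attachment 7, in most of its withhold rows: "Withhold atezolizumab for up to 12 weeks after event onset". Section 10.2 lists among the reasons for which treatment must stop: "The subject missed more than 105 consecutive treatment days due to atezolizumab-related AEs". Sections 6.2 and Attachment 7 permit a longer hold while steroids are tapered, by agreement between investigator and Sponsor. Section 10.2 does not mention tapering.

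**Current status.** Section 6.2.1 opens with an Amendment 7 instruction that atezolizumab toxicities be managed under local approvals and standard care. The older text, including the reference to Attachment 7, follows unchanged.

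**The concern.** Two readers applying different parts of the same protocol could take opposite actions for the same subject. One would end atezolizumab under Section 6.2.1; the other would resume it under Table 16. Similarly, a hold that is still within the limit on one clock can have expired on another, and a taper that Section 6.2 permits can trigger mandatory discontinuation under Section 10.2.

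What is at stake is consistent safety management of a drug given in both arms, and a clear standard against which to judge whether a continued or resumed dose was a deviation. The point still matters for subjects who continue on Sponsor-supplied atezolizumab, because Sections 3.2 and 9.2 still cite Section 10.2 as the stopping rule.

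**Working it through.** **Step 1: severe events, passages side by side.**

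- *Adrenal insufficiency.* The Table 16 row covers Grades 2 to 4 under one withhold-and-resume rule. The hyperthyroidism row of the same table adds a separate line for life-threatening cases, ending treatment permanently. The adrenal row has no such line. A life-threatening immune-mediated adrenal case is therefore stopped under 6.2.1 and resumed on recovery under Table 16.
- *Hyperglycemia and amylase/lipase, Grade 4.* These rows conflict with 6.2.1 only if the event is judged both immune-mediated and life-threatening. Neither row is labelled immune-related, and Table 18 lists immune-related pancreatitis separately, with Grade 4 ending in permanent discontinuation.
- *Other Grade 4 rows.* Pulmonary, hepatic, colitis, hypophysitis, ocular, pancreatitis, myocarditis, dermatologic and neurologic rows agree with 6.2.1 in the table text. They differ only through the rechallenge footnote. Table 23 (nephritis) is not covered here.

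**Step 2: hold limits on one scale (days after the last dose).**

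Inputs: 105 days (Section 6.2), 12 weeks (Attachment 7), more than 105 missed treatment days (Section 10.2), 21-day cycle (Section 6.2).

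The plan's own 105-day figure first: 12 × 7 = 84 days; 84 + 21 = 105; also 5 × 21 = 105. So 105 days equals 12 weeks plus one cycle.

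| Rule | Clock starts at | Calculation | Limit, days after last dose |
|---|---|---|---|
| Section 6.2 | last dose | as stated | 105 |
| Attachment 7 | event onset, day 0 to 21 | onset day + 84 | 84 to 105 |
| Section 10.2, counted from last dose | not stated | as stated | 105 |
| Section 10.2, counted from first missed due dose | not stated | 21 + 105 | 126 |

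**Step 3: does the clock change an actual dosing date?** Take onset on day 10 as an illustration. Attachment 7 expires on day 10 + 84 = 94; Section 6.2 expires on day 105. Under Section 6.2 a missed dose waits for the next planned date, and planned dates fall on multiples of 21, here day 84 or day 105. The last usable date is day 84 on one clock and day 105 on the other, 21 days or one cycle apart. The ±3-day visit window in Section 9.1.4 does not bridge this, since 105 − 3 = 102 is later than 94.

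**Step 4: steroid taper.** Take a hold for an atezolizumab-related event that runs past day 126 because of a taper. Section 6.2 permits it by agreement, as does Attachment 7 for the events it covers. Section 10.2 requires discontinuation whether counting starts at the last dose (limit 105) or at the first missed dose (limit 126). This conflict does not depend on the start date.

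**Step 5: scope.** Section 10.2 counts only events related to atezolizumab; Section 6.2 counts any adverse event that leads to withholding. The two limits therefore apply to different sets of holds as well as different clocks.

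**The case against.** The strongest reply is that Amendment 7 has overtaken these rules. Toxicities now follow local standards, enrollment closed on 25 May 2018, the clinical database is locked, and the study report uses the data reviewed on 23 May 2018. No rewording can alter a decision behind the comparison of arms. That stands, and it limits the point to consistency and to subjects still treated. It does not dispose of it: the conflicting sentences remain in the current text, and the amendment does not say whether local standards replace Attachment 7.

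A second reply is that 6.2.1 is a general rule and Attachment 7 the specific one. The cross-reference supports that reading, but no order of precedence is stated.

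A reader might infer that all Grade 4 immune events are contradicted. The documents do not support this. The definition "Grade 4: Life-threatening or disabling adverse event" in Section 12.1.3 applies only to events not listed in NCI-CTCAE 4.03, and it includes disabling as well as life-threatening events. Table 10 does label Grade 4 as life-threatening, but for daratumumab infusion reactions. Most Grade 4 rows agree with 6.2.1.

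A reader might also infer a fixed spread of 84 to 126 days, or 42 days. Neither end is stated on that scale. The 84 needs onset on the dosing day, and the 126 needs counting from the first missed due dose. With onset on day 21 and counting from the last dose, all three limits give 105. Nor are the limits in 6.2 and Attachment 7 true maxima, given the taper extensions.

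**Conclusion.** The inconsistency is real but narrow. It consists of one clear stop-or-resume conflict (life-threatening adrenal insufficiency), two conditional ones (Grade 4 hyperglycemia and amylase/lipase), a rechallenge provision that 6.2.1 does not acknowledge, hold limits on three clocks, and a taper extension missing from Section 10.2. Between Section 6.2 and Attachment 7 the limits differ by 0 to 21 days for onset within one cycle of the last dose. Section 10.2 either matches Section 6.2 or runs 21 days later, depending on an unstated start date.

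A reader might go further and infer that open-label investigators could choose who continues, and so bias the response-rate comparison. The documents do not show this. The same atezolizumab rules apply to both arms, rechallenge and extended holds need Sponsor agreement, the primary population is intent-to-treat, and nothing indicates how many subjects were affected. No sample-size, power or alpha figure rests on these passages.

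**What to change.** Reconcile Sections 6.2, 6.2.1, 10.2 and Attachment 7 so that:

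- there is one statement for life-threatening or Grade 4 events, with any exceptions named and the rechallenge provision cross-referenced in 6.2.1;
- the maximum hold has one clock with one stated start date, and it is clear whether it covers all adverse events or only atezolizumab-related ones;
- the taper extension is treated the same way in Section 10.2 as in Section 6.2 and Attachment 7;
- the protocol says whether the Amendment 7 instruction on local standards replaces Attachment 7 or sits alongside it.

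Which stopping rule and which limit are right is for the clinical team; this review takes no position. The cost is protocol wording only, with no change to sample size or analysis.

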6.2.1.1. Pulmonary Events

Dyspnea, cough, fatigue, hypoxia, pneumonitis, and pulmonary infiltrates have been associated with the administration of atezolizumab. Subjects will be assessed for pulmonary signs and symptoms throughout the study and will also have CT scans of the chest performed at every tumor assessment.

All pulmonary events should be thoroughly evaluated, as follows, for other commonly reported etiologies such as pneumonia/infection, lymphangitic carcinomatosis, pulmonary embolism, heart failure, chronic obstructive pulmonary disease, or pulmonary hypertension. For specific management guidelines, please see [Attachment 7](#).

6.2.1.2. Hepatic Events

Immune-mediated hepatitis has been associated with the administration of atezolizumab. Eligible subjects must have adequate liver function, as manifested by measurements of total bilirubin and hepatic transaminases, and liver function will be monitored throughout study treatment.

While in this study, subjects who present with right upper-quadrant abdominal pain or unexplained nausea or vomiting should have liver function tests (LFTs) performed immediately and reviewed before administration of the next dose of study drug.

If LFTs increase, concurrent medications, viral hepatitis, and toxic or neoplastic etiologies should be considered and addressed, as appropriate.

For specific management guidelines, please see [Attachment 7](#).

6.2.1.3. Gastrointestinal Events

Immune-mediated colitis has been associated with the administration of atezolizumab.

All events of diarrhea or colitis should be thoroughly evaluated for other more common etiologies. If the event is of significant duration or magnitude or is associated with signs of systemic inflammation or acute phase reactants (eg, increased C-reactive protein [CRP], platelet count, or bandemia), the following are recommended:

- Perform sigmoidoscopy (or colonoscopy, if appropriate) with colonic biopsy with 3 to 5 specimens for standard paraffin block to check for inflammation and lymphocytic infiltrates for confirmation of the diagnosis of colitis.

For specific management guidelines, please see [Attachment 7](#).

6.2.1.4. Endocrine Events

Thyroid disorders, type 1 diabetes mellitus, adrenal insufficiency, and pituitary disorders have been associated with the administration of atezolizumab.

Subjects with unexplained symptoms such as fatigue, myalgias, impotence, constipation, or mental status changes, should be investigated for the presence of thyroid, pituitary, or adrenal endocrinopathies. An endocrinologist should be consulted if an endocrinopathy is suspected. Thyroid stimulating hormone (TSH), triiodothyronine 3 (T3), and free thyroxine (T4) levels should be obtained to determine whether thyroid abnormalities are present. Pituitary hormone levels and function tests (eg, TSH, growth hormone, luteinizing hormone, follicle-stimulating hormone, testosterone, prolactin, adrenocorticotrophic hormone [ACTH] levels and ACTH stimulation test) and MRI of the brain (with detailed pituitary sections) may help to differentiate primary adrenal insufficiency from primary pituitary insufficiency.

For specific management guidelines, please see [Attachment 7](#).

